## **5.2 SECONDARY ENDPOINT(S)**

### **5.2.1 Key secondary endpoint(s)**

The key secondary endpoint of the study is defined in CTP Section 2 as:

*The occurrence of at least one GPP flare (defined by increase in GPPGA score by  $\geq 2$  from baseline and the pustular component of GPPGA  $\geq 2$ ) up to week 48.*

This endpoint is considered as key secondary endpoint for secondary objective (i.e., demonstrate the superiority of spesolimab versus placebo), while for the primary objective (i.e., dose-finding analysis), is considered as secondary in nature only instead of key secondary.

Per CTP Section 7,  
*This (the key secondary endpoint) is a monotone increasing variable, so once a flare has occurred by a particular visit, all subsequent visits will also by definition have had a preceding flare.*

Once the first GPP flare occurs, all subsequent visits will be regarded as the occurrence of GPP flare. The Estimands applied for primary endpoint are also applicable for the key secondary endpoint. The detailed handling of intercurrent events under different Estimands for the key secondary endpoint is described in [Table 5.2: 1](#), which also applies to the secondary and further binary endpoints. The missing data handling for the visits after censoring will be described in [Section 6.6.2](#)

Under the primary Estimand **EM**, for the key secondary endpoint, the occurrence of the first GPP flare (defined by increase in GPPGA score by  $\geq 2$  from baseline and the pustular component of GPPGA  $\geq 2$ ) is a treatment failure while the use of rescue treatment of i.v. spesolimab or use of investigator-prescribed SoC will also lead to treatment failure.

Table 5.2: 1 Summary of handling intercurrent events for binary endpoint during the randomized maintenance treatment period

Intercurrent events	Composite EM	Censoring
Intercurrent event		
Use of rescue medication with i.v. spesolimab	Composite (Treatment failure a )	(
Investigator-prescribed Standard of care to treat GPP worsening	Composite (Treatment failure a )	(
Use restricted medication for other indications	Treatment Policy	(

a Treatment failure indicates the occurrence of GPP flare for key secondary endpoint. For the binary endpoints that indicate positive disease outcome, such as sustained remission, no PSS sub score>1 and DLQI of 0 or 1, the treatment failure indicates that the prespecified endpoint is not achieved.

b Data will be censored (set as missing) after the specified intercurrent event.

### 5.2.2 Secondary endpoints

Three efficacy endpoints and one safety endpoint are defined as secondary endpoints.

Per CTP Section 2, the below-defined secondary endpoints, for the secondary objective of the trial, are included in the formal testing along with the primary endpoint and the key secondary endpoint:

- *Time to first worsening of Psoriasis Symptom Scale (PSS) up to week 48 defined as a 4-point increase in total score from baseline.*
- *Time to first worsening of Dermatology Quality of Life Index (DLQI) up to week 48 defined as a 4-point increase in total score from baseline.*

The Estimands specified for primary endpoint will be applied to the secondary time-to-event endpoints per [Table 5.1:1](#).

For further details on the derivation of the PSS score, and the DLQI score, refer to Sections [10.1.5](#), and [10.1.6](#), respectively.

Per CTP Section 2, the below-defined secondary endpoint, for the secondary objective of the trial, is not included in the formal testing procedure:

[figure not shown]
*Sustained remission, defined as a subject with a GPPGA score of 0 or 1 (clear or almost clear) at all visits up to week 48.*

[figure not shown]
As a binary endpoint, the Estimands applied in key secondary endpoint are also applicable to this secondary endpoint per [Table 5.2:1](#).

Note that, similar as the key secondary endpoint, i.e., the occurrence of GPP flare, the sustained remission is a monotone increasing variable. Once the remission (GPPGA total score 0 or 1) is not achieved or the intercurrent event (can lead to treatment failure) has occurred by a certain visit, the status of sustained remission will be not achieved for all subsequent visits up to week 48.

Per CTP Section 2, the secondary safety endpoint is defined as:

*The occurrence of Treatment Emergent Adverse Events (TEAEs).*

#### **5.4.1 Safety Endpoints**

Safety endpoints are defined per CTP Section 5.2

Intensity of AEs was assessed during the trial according to Rheumatology Common Toxicity Criteria (RCTC) version 2.0. At the time of the data analysis, selected laboratory parameters will be assessed by Common Terminology Criteria for Adverse Events (CTCAE) in addition to RCTC grades, where possible. The specific definition of CTCAE grades is described in [Section 10.3](#)

#### **5.4.2 Demographic and other baseline characteristics**

The following demographic parameters will be defined: sex, ethnicity, race, sub-race of Asian, age, height, weight, BMI, smoking status, and region of sites.

Age [years] will be determined as the difference between year of birth and year of informed consent. BMI will be calculated as weight [kg] / height [m] (based on the last available weight measurement prior to the first randomized dose on V2/D1).

Medical History for GPP include mutation status (IL36RN, CARD14 and AP1S3), as well as the details, if any, on the presence of concurrent chronic plaque psoriasis or chronic erythrodermic psoriasis will be summarized. The method by which diagnosis of GPP was confirmed is also collected.

[figure not shown]
Disease characteristics will include the details on typical flare, most severe flare, longest flare, and most recent flare prior to consent.

Time since first diagnosis [years] will be calculated as the difference between date of first diagnosis and date of informed consent, divided by 365.25. For calculation in the context of incomplete information on the date of first diagnosis, according to [Section 6.6.8](#).

In addition to the mutation status captured via the eCRF, the genes of interest also get re-sequenced. Hereby the mutation status will be defined based on the absence or presence of potential pathogenic IL36RN, CARD14 and AP1S3 variations based on existing functional or potential functional impact of the mutation. Based on this analysis the following groupings may be presented:

- Subjects with a mutation in any of the 3 genes vs. subjects with no mutation at all
- Subjects with a mutation in IL36RN (irrespective of the mutation status in the other genes) vs. subjects without an IL36RN mutation
- Subjects with a mutation in CARD14 (irrespective of the mutation status in the other genes) vs. subjects without an CARD14 mutation
- Subjects with a mutation in AP1S3 (irrespective of the mutation status in the other genes) vs. subjects without an AP1S3 mutation
- Subjects with a mutation in CARD14 or AP1S3 but no mutation for IL36RN vs. subjects not fulfilling this criterion

These re-sequenced results for the mutation status of IL36RN will be the basis for the subgroup classification as described in [Section 6.4](#).

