Trial design	
This is a multicenter, randomized, parallel group, double-blind, placebo-controlled Phase IIb dose finding study to evaluate efficacy and safety compared to placebo with multiple subcutaneous (s.c.) doses of BI 655130/placebo in adolescents from 12 years to less than 18 years of age and adult patients with history of GPP and currently presenting (at screening and at randomization) with a GPPGA score of 0 or 1 (clear or almost clear). Patients will continue to receive randomized maintenance treatment until their last dose at Week 44 if no flare occurs. In the event of a flare, the patient will receive rescue treatment with i.v. open label dose of BI 655130. Upon response of the flare, the patient will continue receiving open label s.c. dose of BI 655130. These patients will receive open-label treatment until 44 weeks after randomization, when the patient will receive the last dose. The maintenance treatment period ends at week 48.
 
The primary statistical analysis of the trial will be performed once all randomized patients have either completed or early discontinued from the 48 week maintenance treatment period.

Total number of patients randomized	
120 including at least 8 adolescent patients aged 12 years to less than 18 years of age evaluable for the primary endpoint (at least 2 adolescents per treatment group)

Number of patients on each treatment	
30 patients on BI 655130 300 mg s.c. q4 weeks (Arm 1) 30 patients on BI 655130 300 mg s.c. q12weeks (Arm 2) 30 patients on BI 655130 150 mg s.c. q12 weeks (Arm 3) 30 patients on placebo (Arm 4)

Diagnosis	
Patients with history of Generalized Pustular Psoriasis (GPP) and currently with GPPGA score of 0 or 1 (clear/almost clear)

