4.1.3 Method of assigning patients to treatment groups

An Interactive Response Technology (IRT) will be used to screen eligible patients, perform drug assignment, manage initial/re-supply ordering of drug supplies and handle emergency un-blinding. The investigator will receive all necessary instructions to access the IRT from the Sponsor. Detailed IRT functions and procedures will be documented in the user requirement specifications mutually agreed to by the sponsor and the IRT vendor.

During Visit 2 and after the patient's eligibility is confirmed, patients will be randomized to blinded treatment arms according to a randomization plan in a 1:1:1:1 ratio. Randomization will be stratified by the stratification factor, concomitant use of systemic GPP medications at randomization (yes versus no) (see [Section 7.4](#)) and the blocking factors, region (Japan versus Non-Japan) and population (Adults versus Adolescents) (see [Section 7.4](#)). The assignment will occur in a blinded fashion via Interactive Response Technology (IRT).

At randomization as well as subsequent medication administration visits (including rescue treatment administration visit (s) with OL BI 655130 in the event that a patient experiences a GPP flare), IRT will assign medication numbers. Note that the medication number is different from the patient number (the latter is generated during screening via the IRT System). Each syringe and vial will have an individual medication number for dispensation.

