The primary analysis of the trial will be done once all patients randomized have either completed or discontinued from 48 weeks of treatment. The primary endpoint analysis may include more than the target number of patients with a GPP flare event. In this situation, it is not planned to perform an additional analysis of the primary endpoint whereby the exact number of target patients with a GPP event only are included.

To support a potential BI 655130 acute GPP flare treatment submission, an interim analysis of the clinical efficacy and safety data collected during the BI 655130 OL i.v rescue and s.c. maintenance treatment periods may be performed. For further details refer to [Section 7.2.7](#).

The stratification factor, concomitant use of systemic GPP medications at randomization (yes or no) and the blocking factors, region (Japan or Non-Japan) and population (Adults versus Adolescents) will be included into the randomization of this trial. The blocking factors of region is implemented to ensure that sufficient patients per treatment group are recruited specifically to support individual country submission in Japan and the blocking factors of population is implemented to ensure there will be paediatric patients randomized to each treatment group to support paediatric investigational plan. The two blocking factors are not intended to be used as an adjustment factor in the primary and key secondary analyses of efficacy (See [Section 7.2](#)).

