## **7.1 DEMOGRAPHIC AND OTHER BASELINE CHARACTERISTICS**

Only descriptive statistics are planned for this Section of the CTR.

Descriptive statistics will be presented by treatment for demographic parameters and baseline characteristics, based on the RS. The systemic GPP medication use at randomisation will be presented by treatment for baseline characteristics as well.

The presence of mutations (yes or no) in the following genotypes will be descriptively presented by treatment for the RS: IL36RN, CARD14, or AP1S3 based on information collected via eCRF and the results for the DNA resequencing respectively.

Characteristics of the trial disease, including details on the past GPP flares prior to trial onset, will be displayed for randomized subjects based on the RS.

For the continuous variables described below, the following categories will be defined, and presented according to the number and percentage of subjects in each category.

Table 7.1: 1 Categories for summary of continuous variables

Variable	Categories
Age	< 50 years 50 to < 65 years ≥ 65 years  Adolescent: age ≥12 years and <18 years Adult: age ≥18 years  < 65 years ≥65 years
Weight	≤70 kg >70 to ≤80 kg >80 to ≤ 90 kg >90 kg  Weight related BE bound < 53.8 kg ≥53.8 to < 91 kg ≥ 91 kg
BMI	< 25 kg/m  25 to < 30 kg/m  ≥ 30 kg/m 
Time since first diagnosis	≤ 1 year > 1 to ≤ 5 years > 5 to ≤ 10 years > 10 years

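### Age derived by subtracting calendar years puts about half of 17-year-olds in the adult row of SAP Table 7.1:1, although the protocol defines and randomises them as adolescents

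*SAP*

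**What the plan says.** SAP Section 5.4.2 gives one derivation of age: "Age [years] will be determined as the difference between year of birth and year of informed consent". SAP Table 7.1:1 then applies the cut-off "Adolescent: age ≥12 years and <18 years Adult: age ≥18 years".

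The protocol synopsis sets the planned number at "120 including at least 8 adolescent patients aged 12 years to less than 18 years of age evaluable for the primary endpoint", with "at least 2 adolescents per treatment group". Protocol Sections 4.1.3 and 7.4 make population (adults or adolescents) a blocking factor run through the interactive response system. The first twelve adolescents have their own equal allocation to the four arms. Protocol Section 7 gives the reason: "the blocking factors of population is implemented to ensure there will be paediatric patients randomized to each treatment group".

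The grouping is then used descriptively. Protocol Section 7.2.2 plans comparisons of the primary endpoint across levels of the stratification and blocking factors, population included. Protocol Section 7.2.3 plans an adult-versus-adolescent comparison of the secondary endpoints in the testing hierarchy. Protocol Sections 7 and 7.4 keep population out of the efficacy models. Protocol Section 8.3.1 lists year of birth, not date of birth, among the items taken from source for the CRF.

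**The concern.** Subtracting years gives completed age only for someone whose birthday has already passed on the day of consent. Everyone else gains a year. At the cut-off of 18 this changes the category: a 17-year-old with a later birthday is tabulated as an adult. The error runs one way. The year difference is never below true age, so nobody aged 18 or over at consent can become an adolescent, and the adolescent row can only lose patients.

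The adolescent group may be as small as 8, or 2 per arm. At that size one misplaced patient halves the adolescent count shown for an arm, and the report appears to show fewer adolescents than the trial randomised. The adolescent data are meant to support a paediatric plan, so a reader of the report would ask about the gap.

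**Working it through.** **Inputs from the documents.** Age rule: year of consent minus year of birth (SAP 5.4.2). Cut-off: 18 (SAP Table 7.1:1). Minimum adolescents: 8 in total, 2 per arm (protocol synopsis). Separate allocation: first 12 adolescents, 1:1:1:1 (protocol 7.4). Screening window: up to 84 days before Visit 2 (protocol 6.2.1).

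**Plan's own figure.** 4 arms × 2 = 8, which matches. The separate allocation gives 12 / 4 = 3 per arm if filled.

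**Example (invented dates).** Born 15 November 2003, consent 1 March 2021. Completed age is 17, an adolescent. Derived age is 2021 − 2003 = 18, an adult.

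**Chance per adolescent.** With birthdays and consent dates spread evenly over the year, half of 17-year-olds have their birthday still to come. So p = P(aged 17) × 1/2. The share aged 17 is an assumption:

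- 1/6 aged 17 (ages even over 12 to 17): p = 1/12 = 8.3%
- 1/20 aged 17: p = 1/40 = 2.5%
- 1/3 aged 17: p = 1/6 = 16.7%

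A simulation with uniform dates agreed: 50.0% of 17-year-olds and 8.3% of adolescents were moved, and no adult was moved the other way.

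**At least one misplaced, 1 − (1 − p)^N, and expected number, N × p:**

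| Share aged 17 | N = 8: expected | N = 8: at least one | N = 12: expected | N = 12: at least one |
|---|---|---|---|---|
| 1/20 | 0.2 | 18% | 0.3 | 26% |
| 1/6 | 0.67 | 50% | 1.0 | 65% |
| 1/3 | 1.33 | 77% | 2.0 | 89% |

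**Some arm shows fewer than 2 adolescents.** With 8 at 2 per arm, any move does this, so the chances are those for N = 8 above. With 12 at 3 per arm, an arm must lose at least 2 of 3: q = 3p²(1 − p) + p³. At p = 1/12, q = 34/1728 = 0.0197, and over four arms 1 − (1 − q)⁴ = 7.6%. At p = 1/40 it is 0.7%, and at p = 1/6 it is 27%.

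**Age at randomisation instead of consent.** Some of the misplaced patients turn 18 before Visit 2. If Visit 2 falls evenly over the 84 days, about 6.54% of adolescents are both misplaced and still under 18 at randomisation (even ages). That gives 1 − (1 − 0.0654)^8 = 42% and 1 − (1 − 0.0654)^12 = 56%.

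**The case against.** The strongest reply is that the visible reach is small. The only place in the public text where derived age drives this split is a baseline table in a section confined to descriptive statistics. A reader might infer that adolescents are also analysed as adults for efficacy. The documents do not show that. Protocol 7.2.2 words the primary-endpoint comparison by levels of the blocking factors, which read plainly means the randomisation grouping. SAP Section 6.4, which the SAP cites for subgroup classification, is not in the public text. Protocol 7.2.3 does not say which variable defines the groups for the secondary endpoints. So the efficacy displays may already be right.

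A reader might also infer that the protocol's minimum of 2 adolescents per arm would be breached. It would not. Protocol 7.4 states it in terms of randomised patients, and a table category cannot change who was randomised. Only the displayed count can fall short.

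Nor do the documents establish that the randomisation system holds the correct group. It must hold a group, because it allocates by it, but no section says how that group is determined. If it were fed year of birth alone, it would make the same error.

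All of this stands, and it limits the point. It does not remove the conflict between the SAP's age rule and the protocol's definition of an adolescent.

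**Conclusion.** The point holds as a minor misclassification in a stated rule. SAP 5.4.2 and Table 7.1:1 together place about half of 17-year-olds in a category that contradicts the protocol's definition. The likely size is 0 to 2 patients. The chance of at least one is 18% to 77% with 8 adolescents and 26% to 89% with 12. With 12 at 3 per arm, the chance that some arm shows fewer than 2 is about 8% (0.7% to 27%). These figures rest on even birthdays and consent dates and on an assumed share aged 17, which the documents do not give.

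The effect is descriptive. Population is not in the efficacy models, so the dose-response test, the log-rank and Cochran-Mantel-Haenszel tests and their error rates are untouched by this split. A reader may notice that age also enters the rule in SAP 7.5.2 that censors patients under 16 at Day 1 for DLQI. If derived age is used there, about half of 15-year-olds would count as 16. Those without a baseline DLQI are still censored at Day 1, so the effect is slight.

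**What to change.** Add one sentence to SAP 5.4.2 or 7.1: in Table 7.1:1 and in every adult-versus-adolescent display, the group is the population factor used for randomisation, corrected only for documented entry errors. Before adopting it, confirm that the system assigns this factor by the under-18 definition and not from year of birth. If SAP Section 6.4 already says this for the subgroup comparisons, a cross-reference at Table 7.1:1 is enough.

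Keep year-difference age for the continuous summary, since the CRF may hold only year of birth. The fix has one small downside: a few patients labelled adolescent may show a derived age of 18, so the table needs a footnote saying why. Otherwise the cost is the one check of the system's definition. No new data are needed.

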## 6. GENERAL ANALYSIS DEFINITIONS

### 6.1 TREATMENTS

For basic study information on the treatment to be administered, assignment to treatment, and selection of dose, refer to Section 3 and 4 of the CTP.

For the analysis of adverse event, the study phases are defined as in [Table 6.1:1](#).

Table 6.1: 1 Flow chart of analysis phases of the study

Study analysis phase	Description	Start (included)	End (included)
Screening phase	Screening	Earliest of (Date of informed consent, first screening procedure)	Date/time of start of the first randomized study treatment minus 1 minute
Randomized maintenance treatment phase	On randomized treatment period	Date/time of start of the first randomized study treatment (V2/D1)	Earliest of i) Date/time of start of the rescue treatment with i.v. spesolimab minus 1 minute. ii) Date of the end of last randomized study treatment + REP  (112 days) at 23:59. iii) Date/time of the first treatment in OLE trial 1368.25 if the subject is rolled over, iv) last contact date on End of Study page at 23:59 if subject is not rolled over.
Flare treatment phase (if applicable)	On flare treatment period	Date/time of start of the first rescue treatment with spesolimab i.v. 900 mg	Earliest of i) Date/time of start of the first OL maintenance treatment minus 1 minute. ii) Date of the end of last rescue treatment + REP  (112 days) at 23:59. iii) Date/time of the first treatment in OLE trial 1368.25 if the subject is rolled over, iv) last contact date on End of Study page at 23:59 if subject is not rolled over
OL maintenance phase (if applicable)	On OL maintenance treatment period	Date/time of start of the first OL maintenance treatment	Earliest of i) Date of the end of last OL maintenance treatment + REP  (112 days) at 23:59. ii) Date/time of the first treatment in OLE trial 1368.25 if the subject is rolled over, iii) last contact date on End of Study page at 23:59 if subject is not rolled over.
Off treatment phase 	Off-treatment period	Date of the end of last study treatment (including randomized treatment, flare treatment and OL maintenance treatment) + REP  (112 days) + 1 day at 0:00	i) Date/time of the first treatment in OLE trial 1368.25 if subject is rolled over, ii) last contact date on End of Study page at 23:59 if subject is not rolled over.

Dates are defined individually per subject. An analysis phase will not extend beyond the start date of the following phase.

 The off-treatment period only exists if the last contact date is after the date of end of last study treatment + 112 days.

 Per CTP Section 7.2.5, all adverse events occurring between start of treatment and end of the residual effect period will be considered ‘treatment-emergent’; the residual effect period (REP) is defined as 16 weeks after the last dose of trial medication. Therefore, 112 days is included in the period

Efficacy analyses ([Section 7.4](#), [7.5](#) and [7.6.1](#)) that are on randomized maintenance treatment phase will take the intercurrent events into account under the concept of Estimand (see [Section 5.1](#), [5.2](#), and [5.3](#))

Treatment groups for the randomized treatment period according to the randomized/actual treatment (see [Table 6.1: 1](#)) will be labelled as follows:

- **"Placebo"** (i.e., randomized to received placebo)
- **"Speso SC Low"** (i.e., randomized to spesolimab 150 mg s.c. q12w)
- **"Speso SC Medium"** (i.e., randomized to spesolimab 300 mg s.c. q12w)
- **"Speso SC High"** (i.e., randomized to spesolimab 300 mg s.c. q4w)
- **"Speso SC Total"**(across spesolimab randomized treatments)
- **"Overall Total"**(across randomized treatments), where appropriate.

“**Speso SC Total**” is applicable in disposition, demographics and baseline characteristics, compliance summaries, AE, clinically significant abnormal lab values and others as deemed necessary.

“**Overall Total**” is applicable in disposition, demographics and baseline characteristics, compliance summaries and others as deemed necessary.

- **"Overall Speso"**(across spesolimab treatments, regardless of i.v. or s.c. treatments), where appropriate.

“**Overall Speso**” is applicable in AE, clinically significant abnormal lab values and others when summarizing the safety outcomes post any spesolimab use.

Treatment groups for the loading dose received on Day 1 of the randomized treatment period according to the randomized treatment (see [Table 6.1: 1](#)) will be labelled as follows:

- **"Speso SC Loading Low "** (i.e., randomized to spesolimab 150 mg s.c. q12w)
- **"Speso SC Loading High"** (i.e., randomized to spesolimab 300 mg s.c. q4w or spesolimab 300 mg s.c. q12w)

Treatment groups for the flare treatment period will be labelled as follows:

- **"Speso IV Total"**(i.e., received at least one flare treatment spesolimab 900mg i.v.)
- **"Speso IV SD"**(i.e., received i.v. flare treatment at Day 1 of flare treatment period)
- **"Speso IV DD"**(i.e., received i.v. flare treatment at Day 1 and Day 8 of flare treatment period)

Treatment groups for OL maintenance treatment period will be labelled as follows:

- "Speso OL SC"(i.e., received at least one OL maintenance treatment)

When applicable, output columns should be arranged in the order as given above.

More details on the technical implementation of these analyses are provided in the ADS Plan of this TSAP.

